#### 10.5.2.3 Secondary safety endpoint analyses

This study is a non-inferiority trial, in which adverse effects of glucocorticoids are expected to be reduced in the low-dose group. The adjustment of multiplicity will not be performed in the analyses on the secondary safety endpoints. The significance level in the hypothesis test will be 5% (two-sided), and confidence intervals to be calculated are two-tailed 95% confidence intervals.

The number of cases in which adverse events and serious adverse events occurred and proportions of those with and without occurrence, etc. are aggregated in a group-by-group manner, and Pearson's chi-square test will be used for intergroup comparisons (or Fisher's exact test, when cells with an expected frequency less than 5 account for 20% or more).

For occurrence of new-onset diabetes requiring treatment, hypertension, dyslipidemia, sleep disorder

requiring treatment, pathological fractures, and infections (intravenous or oral antibiotics are used), the number of cases and proportions of cases with and without occurrence in each group are determined, and Pearson's chi-square test will be used for intergroup comparisons (or Fisher's exact test, when cells with an expected frequency less than 5 account for 20% or more).

For bone density of the lumbar spine, the data will be aggregated using summary statistics for each group, and compared between the groups by the analysis of variance model.

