#### 1.2 Standard therapy for disease being studied

The concomitant use of high-dose glucocorticoids and cyclophosphamide pulse therapy (IV-CY), which is a current standard remission induction treatment, has achieved a high remission rate of 80-90% [2-4]. However, this therapy is associated with a variety of side effects, particularly those attributable to high-dose glucocorticoids, including infections, osteoporosis/aseptic necrosis, hypertension/diabetes/dyslipidemia, cataract/glaucoma, gastric/duodenal ulcer, muscle weakness, menstrual disorder, steroid psychosis, insomnia, and moon-shaped face. Among these side effects, infections are strongly associated with deaths of patients with ANCA-associated vasculitis. In Japan, MPA, which frequently occurs most often in the elderly, account for the majority of ANCA-associated vasculitis, resulting in high mortality from infections compared to other countries, which accounts for approximately half of deaths [13]. Moreover, side effects that are not related to death also affect decreased patients' quality of life and growth in medical costs. Therefore, a new standard treatment with reduced side effects is awaited to be developed.

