## 2.2 Secondary endpoints

[Efficacy]

Time required to achieve remission

Overall survival period, relapse-free interval, time to ESRD, time to occurrence of the first serious adverse event

The proportion of death, relapse, ESRD, and patients with serious adverse events; and proportion of composite outcomes thereof (at 6 and 24 months; \*at 6 months, proportions of death, ESRD, and serious adverse events only)

Proportions of major and minor relapses

Assessment of disease activity using Birmingham Vasculitis Activity Score (BVAS) ver3

Assessment of irreversible damage using Vasculitis Damage Index (VDI) [19]

Evaluation of health-related QOL using SF-36

- 17 -

General assessment of patients using visualized analogue scale (VAS)

Cumulative dose of glucocorticoid

[Safety]

The number of adverse events and serious adverse events and proportion of patients with adverse events and serious adverse events

Proportions of new-onset diabetes, hypertension, and dyslipidemia requiring treatment

The proportion of sleep disorder requiring treatment

The proportion of pathological fractures and bone density of the lumbar spine

The number of infections and proportion of patients with infections that required intravenous or oral administration of antibiotics

[Exploratory]

Immunoglobulin concentration

Whole blood B cell count

Changes in MPO-/PR3-ANCA values associated with treatment, treatment responses, and relapses

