#### 7.6.5 Safety assessments specific to this trial

Among glucocorticoid-related side effects, the number of occurrence and proportion of new conditions that require treatment will be individually assessed separately from general safety assessments. Such conditions include; diabetes, hypertension, dyslipidemia, sleep disorders, pathological fractures, and infections. In addition, bone density of the lumbar spine will be measured to evaluate steroidal osteoporosis (at 0, 12, 24 months).

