## [Safety]

- ① The number of occurrence and proportion of adverse events and serious adverse events that occurred (at 6 and 24 months)
- 2 Proportions of new-onset diabetes, hypertension, and dyslipidemia requiring treatment (at 6 and 24 months)
- ③ Proportion of sleep disorder requiring treatment (at 6 and 24 months)
- ④ Proportion of pathological fractures and bone density of the lumbar spine (at 24 months)
- (5) The number of occurrence and proportion of infections (intravenous or oral antibiotics are used) (at 6 and 24 months)

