#### [Rationale]

To demonstrate the non-inferiority in remission induction rate, the necessary number of cases calculated with the following conditions is 63 in each arm:

 $\alpha = 0.025$  (one-tailed),  $1 - \beta = 0.8$ 

(1)Remission induction rate with rituximab + high-dose glucocorticoids = 0.80

(2)Remission induction rate with rituximab + low-dose glucocorticoids = 0.80

Non-inferiority margin=-0.2

Allocation ratio, 1:1.

With a predicted withdrawal rate of 10%, the target sample size was set as 70 in each arm, a total of 140 cases. The induction rates (1) and (2) are based on RITUXVAS study [8] and the Cambridge University cohort, respectively [14].

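### The number of treated infections is a declared safety endpoint, but the protocol compares arms only on whether a patient had any, so repeat infections do not count in the comparison

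*Protocol*

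**What the plan says.** The protocol's objectives (section 2.2, safety list; likewise the synopsis) name the endpoint as "The number of infections and proportion of patients with infections that required intravenous or oral administration of antibiotics". Section 9.2, under Safety, repeats both parts with time points: "The number of occurrence and proportion of infections (intravenous or oral antibiotics are used) (at 6 and 24 months"). Section 7.6.5 lists infections among the glucocorticoid-related conditions and says that "the number of occurrence and proportion of new conditions that require treatment will be individually assessed separately from general safety assessments".

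The analysis is in section 10.5.2.3. For the listed conditions, infections included, the "number of cases and proportions of cases with and without occurrence in each group are determined, and Pearson's chi-square test will be used" to compare the groups, with Fisher's exact test where expected frequencies are low. On level and intervals the same section says: "The significance level in the hypothesis test will be 5% (two-sided), and confidence intervals to be calculated are two-tailed 95% confidence intervals". There is no multiplicity adjustment.

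The protocol uses the word cases for patients. Section 10.2, for example, says "the target sample size was set as 70 in each arm, a total of 140 cases", where section 3.1 speaks of 140 subjects.

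On importance, section 1.2 says that "infections are strongly associated with deaths of patients with ANCA-associated vasculitis" and attributes about half of deaths in Japanese patients to them. The rationale in section 9.2 calls the glucocorticoid-related safety items a main focus of the study.

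**The concern.** A two-part endpoint has been given a one-part analysis. Once each patient is classed as with or without an infection, the number of infections per patient has gone. No section provides a between-arm comparison of that number. Other quantitative secondary endpoints do have one: analysis of variance for BVAS, VDI, SF-36, VAS and bone density, and a rank-sum test for cumulative glucocorticoid dose.

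The case for the low-dose regimen is similar remission with less glucocorticoid harm, and infection is the harm the protocol stresses most. Both arms also receive rituximab at 6, 12 and 18 months (section 6.3), so repeat infections by 24 months are possible. If they are common, a real reduction in infection burden could be reported as no clear difference, because the chosen test cannot see it.

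**Working it through.** **1. The plan's own figure.** The protocol gives no calculation for infections, so the only figure to reproduce is the sample size. With remission 0.80 in both arms, margin 0.2, one-sided 2.5% and 80% power: n = (1.960 + 0.842)² × 2 × 0.80 × 0.20 / 0.20² = 62.8, so 63 per arm. Then 63 / 0.9 = 70 per arm, 140 in total. This agrees with section 10.2, and 70 per arm is used below.

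**2. What the planned test can and cannot see.** Suppose 28 of 70 patients (40%) are infected in each arm, with on average 2 infections per infected patient in one arm and 1 in the other. The arms then have 56 and 28 infections. The planned table is 28/42 against 28/42, so chi-square = 0 and p = 1. In simulation under this assumption the yes/no test rejects about 5% of the time, its type I error, and a robust count test about 84%. With 1.5 against 1 infection per infected patient, and 30 to 50% of patients infected, the count test rejects 30 to 58%.

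**3. A proportional reduction in all infections.** The protocol gives no infection count per patient, so every mean below is an assumption. Let counts be negative binomial with mean m and dispersion k (variance m + km²), n = 70 per arm, two-sided 5%.

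- Proportion with any infection: q = 1 − (1 + km)^(−1/k).
- Yes/no power: Φ{ [ |q₁ − q₂| − 1.96√(2q̄(1 − q̄)/n) ] / √[(q₁(1 − q₁) + q₂(1 − q₂))/n] }.
- Count power: Φ{ ln(m₁/m₂)/SE − 1.96 }, with SE = √[(1/m₁ + k + 1/m₂ + k)/n].

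Worked case, m = 1.0 against 0.6, k = 0.5. The proportions are q₁ = 1 − 1.5⁻² = 0.556 and q₂ = 1 − 1.3⁻² = 0.408. Yes/no: (0.1473 − 0.1655)/0.0835 = −0.22, power 41%. Count: SE = √(3.667/70) = 0.229 and 0.511/0.229 − 1.96 = 0.27, power 61%. In the control arm 1 − 0.556/1.0 = 44% of infections are repeats.

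| Mean infections, high vs low dose | k | Yes/no | Count | Gain (points) |
|---|---|---|---|---|
| 1.5 vs 0.9 | 0.5 | 43.6% | 72.7% | 29.1 |
| 1.5 vs 0.9 | 1 | 32.1% | 59.4% | 27.3 |
| 1.0 vs 0.6 | 0.5 | 41.3% | 60.7% | 19.4 |
| 1.0 vs 0.6 | 1 | 31.8% | 50.7% | 18.9 |
| 0.8 vs 0.5 | 0.5 | 34.1% | 47.9% | 13.8 |
| 0.8 vs 0.5 | 1 | 26.9% | 40.4% | 13.5 |
| 0.3 vs 0.18 | 0.5 | 24.2% | 27.4% | 3.2 |
| 0.3 vs 0.18 | 1 | 21.5% | 25.3% | 3.8 |
| 0.25 vs 0.15 | 0.5 | 21.6% | 23.9% | 2.3 |
| 0.25 vs 0.15 | 1 | 19.6% | 22.4% | 2.8 |

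Simulation agrees: 32–42% against 52–60% for 1.0 vs 0.6, and 19–21% against 21–23% for 0.25 vs 0.15. Around a control mean of 0.3 it shows a gain of 2 to 3 points, slightly below the formula.

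**4. The 6-month time point.** At a constant rate, 1.0 and 0.6 over 24 months become 1.0/4 = 0.25 and 0.6/4 = 0.15 at 6 months. That is the last pair of rows, where the gain is small.

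**5. The protocol's only infection frequency.** Section 8.5 lists infection in 7/99 patients (7%) in an earlier trial of rituximab with high-dose glucocorticoids. This is a proportion of patients, not a count. At about 7% infected in the control arm and a rate ratio of 0.6, simulation with the protocol's chi-square/Fisher rule gives about 7% power, against 3–4% for the robust count test. Both are useless there, and the count test is slightly worse.

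**The case against.** **Left to the statistical analysis plan.** Section 10.5 calls its methods the major ones and defers further detail to that plan, which is not shown and may add a count analysis. A secondary safety count may also legitimately be tabulated without a test. This limits the point but does not remove it. Section 10.5.2.3 is not silent on infections: it names the variable and the test, and together they cover half of the declared endpoint.

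**The size rests on assumed rates.** This stands. The large gains need roughly 44% or more of control patients infected. At the 6-month level, where the schedule-fixed glucocorticoid contrast lies and the first analysis is made, the gain is a few points. Near 7% infected there is none.

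**Stronger readings that the protocol does not support.** A reader might infer that fatal infection drops out of the comparison. It does not: a patient whose first treated infection is fatal is counted as infected, and death, overall survival and serious adverse events are analysed separately. A reader might also extend the point to all adverse events, arguing that nearly every patient will have one, so that the yes/no split is uninformative and a severity-grade comparison is needed. The protocol gives no rate to support that. Its adverse-event sentence is also left open-ended, and serious adverse events are already compared.

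**Conclusion.** The mismatch holds on the protocol's text at any infection rate: the number of treated infections is declared for 6 and 24 months, and the fixed between-arm analysis uses only the proportion of patients infected. What is lost is the contribution of repeat infections. It is a secondary endpoint without multiplicity control, so the non-inferiority conclusion is untouched.

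The practical size is conditional. With 70 per arm, dispersion 0.5 to 1, a rate ratio of about 0.6 and assumed means, a count analysis adds about 13 to 30 points of power at 0.8 to 1.5 control infections per patient over 24 months. It adds about 2 to 3 points at 0.25 to 0.3 per patient, and none or slightly less than none near 7% of patients infected. The protocol does not show which of these situations applies. The change is worth making because it completes a declared endpoint at little cost, mainly for the 24-month analysis.

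**What to change.** In section 10.5.2.3, add a between-arm comparison of the number of antibiotic-treated infections per patient to 24 months, and to 6 months as declared. Use negative binomial regression, or Poisson regression with robust variance, with terms for arm and the allocation factors (age, eGFR, ANCA type) and log observed time as offset. Report the rate ratio with its 95% CI. Keep the proportion of patients infected, with the chi-square or Fisher test, beside it.

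The cost is some wording and one further model at each time point, on adverse-event data already collected. The one real addition is a rule, set before the data are fixed, for when a new infection episode starts. Section 8.2 lists a date of occurrence and an outcome category for each event but no resolution date, so separating a new infection from a persisting one is not automatic. If infections prove rare, the count model will add little and its interval will be wide.

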## **10.5.3 Exploratory analyses**

For eGFR, IgG, and B cell count, their changes over time will be described with summary statistics for each group, and compared between the groups by the analysis of variance model. eGFR values will be calculated with the MDRD equation [17] (to be corrected with the coefficient for Japanese), and patients receiving dialysis will be assumed to have eGFR =  $0 \text{ ml/min}/1.73\text{m}_2$ .

For B cells being depleted/recovered, MPO-/PR3-ANCA remaining positive/turning to negative, and prednisolone discontinuation/continuation, the number of cases and proportion will be determined for each group, and Pearson's chi-square test will be used for intergroup comparisons (or Fisher's exact test, when cells with an expected frequency less than 5 account for 20% or more).

For time to B cell recovery, an analysis of competing risks will be performed.

## **11. Adherence to and Deviation from Protocol**

- The principal investigator or co-investigators should document any procedure deviating from the Protocol regardless of the reason for the deviation.
- (2) For any deviation from the Protocol that occurred for a medically compelling reason, such as avoidance of an imminent danger to the subject, the investigator should describe details and the reason of the deviation in the Status Report of this study, and submit the report to the head of the institution every fiscal year.

## 12. Modifications to Protocol and Case Report Form

## 12.1 Revision of protocol and case report form

- (1) When the principal investigator finds it necessary to revise the Protocol and Case Report Form, the investigator shall promptly submit the revised Protocol and Case Report Form to the head of the institution and obtain the approval promptly from the IRB through the head of the institution.
- (2) The same procedure shall be followed when instructions by the head of the institution based on opinions of the IRB are acceptable to the investigator and the Protocol and Case Report Form are to

be revised accordingly.

## 13. Termination, halt, or completion of the study

## 13.1 Criteria for terminating or halting the study

- 1) The principal investigator examines the appropriateness of the trial continuation when:
  - 1. Critical information has been obtained on the quality, safety, or efficacy of the study medication;
  - 2. Recruitment of study subjects are difficult, and the achievement of target case number is deemed to be difficult.
  - 3. The IRB issued an instruction to modify the Protocol, and the instructed modifications are deemed to be difficult to accept.
- 2) The study will be terminated when the IRB issued a recommendation or instruction of termination.
- The coordinating investigator examines the abovementioned matters to decide whether the study should be continued.
- 4) When the investigator decided to terminate or halt the study, the investigator should report the decision and underlying reasons promptly in writing to the head of the institution.

## 13.2 Study completion

After the completion of the study, the principal investigator shall submit a written notice of the study completion and a written report summarizing the results from the study to the head of the institution.

#### 14 Data Handling and Storage of Records

Detailed data management procedures are described in the Data Management Plan.

## 14.1 Data collection

All the data related to this trial will be transcribed to the Case Report Form (CRF) after anonymization. Clinical study data on CRFs are extracted from source documents, and must be consistent with the contents of the source documents. The principal investigator or co-investigators should prepare CRFs using a software compatible with requirements of 21 CFR Part 11, GCP ministerial ordinances, and ER/ES guidelines. When any modification, correction, or addition is made to the CRF contents, the principal investigator or co-investigators should use the software that was used to create the CRF, and all changes should be recorded as electronic information. It should be noted that any CRF prepared by a co-investigator or CRF containing data that have been transcribed from the source documents (source data) by a study

collaborator is subject to content verification by the principal investigator before submission to ensure the absence of any problem. The principal investigator ultimately provides the institution with electronic CRFs (copy) in an electronic medium (e.g., CD-R). The principal investigator ensures the readability and storage stability of the electronic CRFs (copy).

## 14.2 Retention and submission of source documents and other records

The principal investigators of each site keep essential documents related to the implementation of the trial (duplicate copies of application documents, notifications from the hospital director, duplicate copies of various application forms and reports, list of subject identification codes, informed consent forms, duplicate copies of case report forms, and other documents and records that are necessary to ensure the reliability of the data), and retains them for at least five years after the end of the study.

In this study, source documents (source data) refer to the following documents and the like.

- (1) Records of subjects' consents and information provided to subjects
- (2) Records, which are the basis of CRF contents, such as medical records, nursing records, clinical laboratory test data, and imaging films. Note that data stored in electronic medical records are also regarded as source documents.
- (3) Records related to administration of the study medications.
- (4) Trial-related documents or records pertinent to tests required for GCP

Among the data documented in the CRF, the source documents (source data) for the following items are descriptions in CRF themselves. However, if they are also described in medical records or the like, said medical records or the like are deemed to be the source documents (source data).

- (1) Purpose of concomitant medication/treatment
- (2) Adverse event information on grade, outcomes (including follow-up results), severity, and judgment and rationale for causal relationships between the study medication and glucocorticoids
- (3) Reasons for subjects to have discontinued trial participation
- (4) Principal investigator's or co-investigator's comments
- (5) BVAS and VDI

#### 15 Ethical matters

#### **15.1 Ethical matters**

This study shall be conducted in compliance with ethical principles based on the Declaration of Helsinki and ethical guidelines for clinical research and in accordance with ICH-GCP and other relevant local regulatory requirements.

## 15.2 Adherence to the protocol

Researchers participating in this study adhere to the Protocol as long as patients' safety and human rights are endangered.

## 15.3 Approval from the Institutional Review Board

#### **15.3.1** Approval at the start of study participation

To participate in this trial, each institution must approve that the trial will be conducted using this Protocol and the information document for patients. When the approval is obtained, the site coordinator at each institution sends a duplicate copy of the approval document to the case registration center (DM Office, Clinical Research Center, Chiba University Hospital). The principal investigator of the site retains the original approval document, and the case registration center retains the duplicate copy (see 4.5(1) for sending procedure). Each institution can modify the information document for patients independently, without deviating from the scope of requirements for the clinical trials, and use it after the institutional approval. However, institutions are not allowed to introduce any institution-specific modification to contents of the Protocol. The common Protocol must be used by all participating institutions. When any modification of the contents is required, an amendment or revision will be made to the common Protocol used by all institutions. Therefore, when a modification of the protocol text is requested by an institution, the site coordinator consults the Trial Coordinating Office. When the information document is modified in response to an instruction or the like of the institution, the modified document should be sent to the Trial Coordinating Office. The Trial Coordinating Office can request the institution to reconsider the modification request (deletion or content change) through the principal investigator of the site, if such modifications are considered inappropriate.

## 15.3.2 Annual renewal of the institutional approval

The review/approval of this Protocol and the patient information document by each institution may or may not be subject to annual renewal according to the rule of each institution. Even if they have undergone annual renewal, the Trial Coordinating Office does not require the renewed approval be sent from each applicable institution.

